7.4. Definition of RLS Refractory to Medication (IC #2)

For inclusion criterion #2, the following definition of refractory will be used:

The patient has failed at least one prescription medication administered to treat RLS* for one or more of the following reasons, as determined by the investigator:

- 1. Adverse effects associated with the medication are intolerable.
- 2. Patient exhibits symptoms of augmentation.
- 3. Efficacy has reduced to the point where an up titration would be needed to maintain a sufficient response to medication.

NOCTRIX H E A L T H

Clinical Trial

Investigational Plan, Protocol CT-05 (Extension Study)

Document #: CT-4

Rev: 1.0

Effective: 11/24/2021

- 4. The patient lacks sufficient response to medication at the maximum approved or recommended dosage.**
- 5. The patient lacks sufficient response to medication at the maximum tolerable dosage due to adverse effects.

*Failure of any of the following prescription medications is sufficient to demonstrate that a patient is refractory: Ropinirole (FDA-approved), Pramipexole (FDA-approved), Rotigotine (FDA-approved), Gabapentin enacarbil (FDA-approved), Pregabalin (not FDA-approved for RLS, but administered in clinical practice), Gabapentin (not FDA-approved for RLS, but administered in clinical practice).

** per FDA-approved dosage regimen or per RLS consensus statement in the case of off-label medications (Pregabalin or Gabapentin).

8. Investigational Device

8.1. Description

The NTX100 Neuromodulation System is positioned and worn bilaterally on the legs with stimulation electrodes over the head of the fibula bone, thus targeting the common peroneal nerve – this nerve target innervates regions of the lower extremities commonly associated with RLS symptoms. For each leg, the NTX100 Neuromodulation System consists of (1) one stimulation unit, (2) two or more electrode areas, and (3) a mechanism for attachment to leg, described below.

- The (1) stimulation unit will:
 - o be battery-powered and contain a rechargeable battery and connector for recharging,
 - o contain a circuit board that generates the stimulation waveform,
 - o contain controls that the subject can use to activate stimulation,
 - contain controls that the subject can use to adjust the intensity of stimulation within a range programmed by the researcher,
 - contain an electronic connection mechanism to deliver a stimulation waveform to the electrodes,

NOCTRIX H E A L T H

Clinical Trial

Investigational Plan, Protocol CT-05 (Extension Study)

Document #: CT-4

Rev: 1.0

Effective: 11/24/2021

- contain an interface that the researcher can use to program the range of stimulation intensities, program the mode of stimulation (active or sham), and download data on compliance and functionality.
- The (2) electrodes areas will each:
 - o be an electrolyte-containing medium or a hydrogel material,
 - be disposable, allowing for at least 1 night of use by one subject,
 - be attached to the stimulation device by using snaps, magnetic connectors, conductive adhesives, shielded or insulated wires, hook and loop fasteners, or similarly secure connectors,
 - have an electrode surface area between 5cm2 and 50cm2.
- The (3) attachment mechanism will:
 - secure the device containing the disposable electrode areas to the body via straps and/or additional biocompatible adhesives.

Description of stimulation parameter ranges allowed by protocol:

Pulse amplitude: up to 45mA

Frequency: 2kHz - 6kHz

Pulse width: 80 - 250 microseconds (depending on frequency)

Duty cycle: 25-100%

Pulse shape: Charge-balanced

Duration: up to 60 minutes per session (up to 120 minutes per day)

8.2. Instructions for Use and Administration

Use of the NTX100 Investigational device is described briefly herein. For details see Instructions for Use.

8.2.1. Route of administration

The NTX100 Neuromodulation System is designed to stimulate the common peroneal nerve; stimulation electrodes within the device are positioned superficially and bilaterally on the lower

Investigational Plan, Protocol CT-05 (Extension Study)

Document #: CT-4

Rev: 1.0

Effective: 11/24/2021

legs over the head of the fibula bone, a position where the peroneal nerve is close to the skin. This nerve target innervates regions of the lower extremities commonly associated with RLS symptoms.

8.2.2. Dosage and dosage regimen

The dosage regimen depends on the intensity, timing, and duration of stimulation:

- 1. Intensity. The setpoint stimulation intensity may be the lesser of (a) the maximal intensity that the subject reports is non-distracting and comfortable, as determined in the calibration session described in the instructions for device use and (b) the maximal intensity for each set of stimulation parameters, as determined based on device output capabilities. Subjects may be allowed to adjust stimulation intensity from the setpoint stimulation intensity, but only within a limited pre-programmed range. For example, the subject may increase intensity if symptoms are severe or reduce intensity if symptoms are mild.
- 2. Timing. Subjects may be instructed to administer stimulation primarily after RLS symptoms become noticeable and before the RLS symptoms become severe.
- 3. Duration. Each session of stimulation may last 30 minutes. Stimulation may be activated for up to 120 minutes per day (e.g., up to 4 x 30-minute sessions), depending on the timing, duration, and severity of RLS symptoms for the specific subject.

8.3. Contraindications

The following are contraindications to device usage:

- Diagnosis of epilepsy or other seizure disorder,
- Active medical device implant anywhere in the body, including but not limited to pacemakers, spinal cord stimulators, deep brain stimulators
- Metal implant at the site of study device application
- Known allergy to device materials (or severe previous reaction to medical adhesives or bandages)
- Cellulitis, open sores, or acute injury at or near the location of device electrode application

Investigational Plan, Protocol CT-05 (Extension Study)

Document #: CT-4

Rev: 1.0

Effective: 11/24/2021

9. Risks

9.1. Investigational device risks

NPNS devices such as NTX100 Neuromodulation System result in a known potential for the following anticipated observations, which are typically mild to moderate, transient in nature, and resolve over time.

- Mild skin irritation from use of adhesive electrodes and/or secondary attachment mechanism.
- Discomfort, paresthesia, or otherwise irritating or uncomfortable sensations during active electrical stimulation.
 - This risk is reduced by calibrating the stimulation intensity.
- Temporary interference with sleep while wearing the device:
 - For some individuals, device may be uncomfortable, thus interfering with sleep while wearing the device.
 - For some individuals, this device may interfere with preferred sleep positions, thus interfering with sleep during usage.
- Temporary increase in RLS symptoms while wearing the device:
 - For some individuals, this device may interfere with voluntary leg movements used to relieve RLS symptoms, thus leading to a temporary increase in RLS symptoms.
 - In some cases, this device may otherwise lead to a temporary increase in RLS symptoms during active stimulation for other reasons.
 - This risk may be reduced by calibrating the stimulation intensity and/or adjusting the schedule of stimulation.

10. Adverse Events

Anticipated observations (e.g. common treatment effects) and adverse events occurring during the study will be recorded. Descriptions of anticipated observations and AEs will include the date of onset, the date it ended, the severity, the relationship to study device, and the outcome. All reported AEs

NOCTRIX H E A L T H

Clinical Trial

Investigational Plan, Protocol CT-05 (Extension Study)

Document #: CT-4

Rev: 1.0

Effective: 11/24/2021

will be summarized by the number of subjects reporting AEs, system organ class (where applicable), severity, seriousness, and relationship to study device.

The study Investigator and Coordinator will evaluate, characterize and record in the electronic Case Report Form (eCRF) all adverse events (AEs) occurring in all subjects from the time of enrollment to study exit (or premature withdrawal). Adverse events unresolved at study exit will be followed by the Investigator until resolution occurs or at least 30 days after the subject's participation in the study is complete. AEs may be reported spontaneously by the subject or detected by the Investigator or Coordinator. AEs should be evaluated for diagnoses not just symptoms (i.e., "angina", not "chest pain").

In addition to verbatim terms, the Sponsor may categorize all AEs using MedDRA preferred terms (PT) and system organ classes (SOC). Analysis may report both verbatim and MedDRA terms.

10.1. Adverse Event Definitions

An **adverse event** (AE) is any untoward medical occurrence, independent of its association with the investigational device. AEs also include any adverse laboratory signs or physical exam findings.

A serious adverse event (SAE1) is any AE that:

- led to a death,
- led to a serious deterioration in the health of the subject that:
 - resulted in a life-threatening illness or injury,
 - resulted in a permanent impairment of a body structure or a body function,
 - required in-patient hospitalization or prolongation of existing hospitalization,
 - resulted in medical or surgical intervention to prevent permanent impairment to body structure or a body function
- or led to fetal distress, fetal death or a congenital abnormality or birth defect.

A **device-related SAE** is an event meeting the SAE definition above that is also rated as probably or definitely related the investigational device. No device-related SAEs have been reported in prior

¹ Definition from ISO14155:2011

Investigational Plan, Protocol CT-05 (Extension Study)

Document #: CT-4

Rev: 1.0

Effective: 11/24/2021

studies. Note that an elective or pre-planned hospitalization for a condition that did not worsen during the study is not an AE.

An **unanticipated serious adverse device effect** (USADE) is any SAE that is caused by, or associated with, a device, if that effect, problem, or death was not previously identified in nature, severity, or degree of incidence in the investigational plan or application (including a supplementary plan or application).

10.2. AE Severity and Relatedness

Each AE occurring in the study will be characterized by the study Investigator as to severity (Table 1) and relatedness (Table 2).

Table 1. AE Severity Grading System.

Grade	Brief description
Grade 1	Mild; asymptomatic or mild symptoms; clinical or diagnostic observations only; intervention not indicated
Grade 2	Moderate; minimal, local, or non-invasive intervention indicated; limiting ageappropriate instrumental ADL ^a
Grade 3	Severe or medically significant but not immediately life-threatening; hospitalization or prolongation of hospitalization indicated; disabling; limiting self-care ADL ^b
Grade 4	Life-threatening consequences; urgent intervention indicated
Grade 5	Death related to adverse event

^a'Instrumental ADL' refers to activities of daily living such as preparing meals, shopping for groceries or clothes, using the telephone, and managing money. ^b'Self-care ADL' refers to bathing, dressing and undressing, feeding oneself, using the toilet, taking medications, and not being bedridden. From the National Cancer Institute Common Terminology Criteria for Adverse Events v4.0 NCI, NIH, DHHS. May 29, 2009 NIH publication #- 09-7473.

Table 2. AE Relatedness Grading System.*

Investigational Plan, Protocol CT-05 (Extension Study)

Document #: CT-4

Rev: 1.0

Effective: 11/24/2021

Grade	Relationship of AE to study device	Description
5	Definite	An event that follows a reasonable temporal sequence from administration of the study device; that follows a known or expected response pattern to the study device; and that is confirmed by improvement on stopping.
4	Probable	An event that follows a reasonable temporal sequence from administration of the study device; that follows a known or expected response pattern to the study device; and that is unlikely to have been caused by concurrent/underlying illness or other drugs, procedures, or other causes.
3	Possible	An event that follows a reasonable temporal sequence from administration of the study device; that follows a known or expected response pattern to the study device; but may have been caused by concurrent/underlying illness, drugs, procedure, or other causes.
2	Unlikely	An event that does not follow a reasonable temporal sequence from administration of the study device; that does not follow a known or expected response pattern to the study device, or most likely was caused by concurrent/underlying illness, drugs, procedure, or other causes, because of their known effects.
1	Not related	An event almost certainly caused by concurrent/underlying illness, drugs, procedure, or other causes.

^{*} AEs occurring before treatment with the study device will be categorized as unrelated to the study device.

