8.3 Safety Analyses

The proportion of subjects having one or more adverse events (AEs) between study entry and Week 24 will be presented by Arm. The proportion of subjects reporting AEs between Week 25 and Week 32 will be presented for Arm 1. Similar analyses will be done for serious adverse events (SAEs), device-related SAEs, and device-related AEs

Adverse events will be coded using the Medical Dictionary for Regulatory Activities (MedDRA). AEs will be summarized at the subject level using counts and percentages by MedDRA system organ class (SOC) and preferred term (PT). AEs will also be summarized at the event level using

counts and percentages by SOC/PT and seriousness, by SOC/PT and severity, and by SOC/PT and relationship to the device.

Frequency charts of adverse events occurring at any time during the study will be produced. The proportion of subjects with at least one AE will be presented overall and by SOC. The proportion of subjects with at least one occurrence of individual AEs will be presented for AEs occurring in >3% of subjects overall or within either Arm.

This document, when printed, is valid only until its new revision gets released, or when it becomes obsolete in the eQMS. The user of a printed copy of this document is responsible for using the current revision and for discarding superseded or obsolete revisions. The most current version of this document always resides in the eQMS.

Noctrix Health, Inc. CONFIDENTIAL CL-7 v2.0

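### Protocol Table 2 makes a known or expected pattern a condition for Possible, Probable and Definite, so a device effect of unforeseen nature cannot enter the device-related SAE count

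*Protocol*

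**What the plan says.** Protocol Section 10.2 has the investigator grade every AE for relatedness on the five-level Table 2. The top three grades each ask for reasonable timing, then add:

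- Definite (5): "that follows a known or expected response pattern to the study device; and that is confirmed by improvement on stopping".
- Probable (4): "that follows a known or expected response pattern to the study device; and that is unlikely to have been caused by" another source.
- Possible (3): "that follows a known or expected response pattern to the study device; but may have been caused by" another source.

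Unlikely (2) covers an event lacking reasonable timing, one "that does not follow a known or expected response pattern to the study device, or most likely was caused by" another source. Not related (1) needs an almost certain other cause.

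Two definitions in Section 10.1 bear on this scale. A device-related SAE is an SAE "that is also rated as probably or definitely related the investigational device". A USADE is an SAE caused by or associated with the device whose effect "was not previously identified in nature, severity, or degree of incidence in the investigational plan".

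The grade feeds the results. SAP Section 8.3 presents the proportion of subjects with AEs and adds: "Similar analyses will be done for serious adverse events (SAEs), device-related SAEs, and device-related AEs". Neither document says which grades make a non-serious AE device-related.

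**The concern.** Relatedness is a judgement about cause. Expectedness is a judgement about whether the effect was already known. Table 2 makes the second a precondition for the first, so the count meant to show harm from the device excludes harms of a new kind by rule rather than by evidence.

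This matters in an extension study. Section 16.1 says subjects had 4 or 8 weeks of device use in RESTFUL, and Arm 1 adds 24 weeks. Section 10.1 notes that no device-related SAEs were reported in prior studies. If that statement is repeated for CT-05 from grades assigned under this table, it would say less than it appears to about SAEs of unforeseen nature.

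**Working it through.** No figure in the plan needs reproducing. The check is a logic table built from Protocol Table 2.

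**Inputs.** Four features of an event: reasonable timing (yes/no), recognised pattern (yes/no), improvement on stopping (yes/no), and strength of another cause (unlikely, may, most likely, almost certain).

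**Rules.**
- Definite = timing AND pattern AND improvement on stopping.
- Probable = timing AND pattern AND other cause unlikely.
- Possible = timing AND pattern AND other cause may explain it.
- Not related = other cause almost certain.
- Unlikely can be read two ways. *Reading A*: any one of its conditions suffices. *Reading B*: timing and pattern are both absent, or another cause is most likely.

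**Case of interest.** Timing is good and the pattern is not recognised. That leaves 2 × 4 = 8 combinations. Improvement on stopping enters only Definite, which already fails for want of a pattern, so the yes and no rows coincide:

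| Other cause | Combinations | Possible, Probable or Definite | Reading A | Reading B |
|---|---|---|---|---|
| unlikely | 2 | none | Unlikely | no grade |
| may | 2 | none | Unlikely | no grade |
| most likely | 2 | none | Unlikely | Unlikely |
| almost certain | 2 | none | Unlikely and Not related | Not related |

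So 0 of 8 reach Possible under either reading. Under A, all 8 fit Unlikely. Under B, the 4 combinations in which the device is a credible cause (first two rows) match no grade.

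**Contrast.** Take an event with good timing, improvement on stopping and other cause unlikely. With a recognised pattern it meets both Definite and Probable. Without one it is Unlikely (A) or ungraded (B). The causal evidence apart from the pattern is identical.

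**Carry-through.**
1. A device-related SAE needs grade 4 or 5 (Section 10.1), so an SAE without a recognised pattern cannot be one.
2. The USADE definition includes SAEs unforeseen in nature and refers to no Table 2 grade. Such an SAE can be a USADE, yet it is absent from the device-related SAE count.
3. This applies to nature only. A recognised effect that is unforeseen in severity or incidence can still be graded 4 or 5.
4. For device-related AEs, the exclusion follows if the cut-off is grade 3, 4 or 5. With no cut-off stated, it is conditional.

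**The case against.** The strongest reply is that the plan has other safeguards and that the wording can be read more generously. Much of this stands.

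- *Sponsor review.* Section 13.7 has the sponsor review all AEs, confirm the site's relatedness grading, discuss disagreements and investigate each SAE for USADE status. Section 14.2(h) adds investigation of unanticipated device-related effects. A reader might infer that non-serious new effects have no protection; these sections show otherwise. But no relatedness criteria besides Table 2 are given, so confirming a grade leads back to the same rule.
- *Visibility.* A reader might infer that these events disappear from the results. They do not. SAP Table 4.5 sets out AEs at every level of relationship, Listing 4 lists AEs for the Safety Analysis Population, and Section 8.3 gives AE proportions by Arm regardless of grade. What is affected is the device-related summary.
- *Meaning of expected.* Table 2 does not define the term or tie it to the effects listed in Section 9.1. A reader might infer that anything outside that list is capped. A site could fairly count effects predicted by the mechanism: foot weakness in the stimulated nerve's territory is arguable, because the device targets the peroneal nerve and activates lower-leg muscle (Sections 1.4 and 1.5). This narrows the problem, but leaves grading to how each of seven sites (SAP Section 5.5) reads one word.
- *Purpose.* The stated objective is longer-duration efficacy, tolerability and adherence, not detection of new harms. That limits how much weight the point carries, but does not affect the logic.

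**Conclusion.** The point holds. On the literal text, an event without a known or expected pattern cannot be graded Possible or higher. An SAE of unforeseen nature can therefore be a USADE but not a device-related SAE. That step rests only on Table 2 and the two definitions in Section 10.1. Extending it to device-related AEs assumes a cut-off at Possible or higher. Saying such events are placed in Unlikely, rather than left ungraded, assumes Reading A.

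The size in events cannot be calculated, since the documents give no counts by grade, and a site that reads expected as mechanistically plausible would avoid part of the loss. It would be too strong to say that the device-related results can only confirm known effects, or that a finding of no device-related SAEs is guaranteed: recognised effects at new severity or frequency can still be counted. The classification rule should be corrected. The efficacy analyses are not affected.

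**What to change.** 1. **Grades 3 to 5.** Keep the pattern clause but give it an alternative: *or is otherwise plausibly explained by the stimulation, electrodes or attachment*. Leave the timing, other-cause and improvement-on-stopping criteria as they are. Improvement on stopping should not itself be the alternative, because any well-timed, self-limiting event would then meet the condition.
2. **Grade 2.** Remove absence of a known pattern as sufficient on its own, and make clear how the remaining conditions combine.
3. **Section 10.2.** State that expectedness is judged separately from relatedness, at the USADE decision.
4. **SAP Section 8.3.** State the grade cut-off for a device-related AE.
5. **Events already graded.** If any were rated Unlikely solely because they were unexpected, have the investigator re-assess them under the revised wording, and report both the initial and the revised grade.

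The cost is table wording, one SAP sentence and a note to sites. Endpoints and visits do not change. Device-related AE and SAE counts may rise. Re-assessment would be made in an open-label study by assessors who know the treatment, which is why both grades should be shown.

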10.3. Adverse Event Reporting

Investigators must report all SAEs to the study Sponsor and governing IRB within 3 business days or according to local IRB guidelines. Investigators should call the study sponsor immediately upon becoming aware of the occurrence of an SAE. The sponsor will contact the independent medical reviewer, to assist in assessing any safety concerns, if needed. The Investigator should be able and willing to provide further information on the specific event when requested by the study Sponsor. If the Investigator learns of an SAE that occurs within 1 month after the subject completes the study,

Investigational Plan, Protocol CT-05 (Extension Study)

Document #: CT-4

Rev: 1.0

Effective: 11/24/2021

he/she should notify the Sponsor. Investigators must also report all AEs to the governing IRB as determined by that IRB.

Prompt AE evaluation:

- protects the safety of study subjects;
- aids in understanding the overall safety profile of the device;
- prompts, if necessary, modification to the study protocol
- allows improvements in study design or procedures; and
- adheres with standard good clinical practices.

11. Device Tracking

The Sponsor will send the investigational devices to the Investigator. The Investigator must house study devices in a secure location.

The Investigator must carefully and completely track receipt, use and disposition of all investigational devices. The Sponsor will track sending and receiving of devices. The Sponsor will monitor site device accountability periodically.

If a Sponsor representative or designee is present at the time of use, he/she may directly take possession of used device(s). All devices will be returned to the Sponsor after the study is complete.

The investigational device may include components that are consumable or semi-consumable and may be replaced on a periodic or as-needed basis. Such device replacement can occur via an inperson exchange or via delivery to the subject via courier from the site.

12. Device Deficiencies and Malfunctions

Throughout the study, the Investigator and study staff will report and document all device deficiencies and malfunctions related to the identity, quality, durability, reliability, safety or performance of the device. This includes reporting of device deficiencies/malfunctions that did not lead to an AE but could have if: 1) suitable action had not been taken, 2) intervention had not been made, or 3) circumstances had been less fortunate. If possible, the Investigator should return devices suspected of deficiency or malfunction to the Sponsor for analysis.

Investigational Plan, Protocol CT-05 (Extension Study)

Document #: CT-4

Rev: 1.0

Effective: 11/24/2021

13. Ethical and Regulatory Considerations

